**Envafolimab combined with chemoradiotherapy in
the full neoadjuvant treatment of pMMR / MSS
locally advanced rectal cancer**

**Single-arm, single-center, exploratory, phase II,
clinical study**

study protocol

**Protocol version number: V1.1
Version date: March 02, 2023**

**Study director: Chief [name]
Associate [name]
Research unit: Yunnan Provincial Cancer Hospital**

Scheme signature page

I, as the physician / statistical analyst involved in the study, have read the protocol for this study.

I have fully discussed the purpose of the study and the content of the protocol.

I agree to conduct the study under this protocol, to comply with the ethics requirements, and to conduct this clinical study under the guidance of Good Clinical Practice (GCP).

I agree that the contents of this protocol are confidential and will not be disclosed to third parties, and the contents of the protocol are only treatment for this study.

I understand that if the decision to prematurely terminate or suspend it is made at any time and for any reason, I will be informed in writing. Similarly, if I decide to withdraw from the study, I will immediately notify the study leader and the principal investigator.

Name: _____

Signature: _____

Date: _____

Protocol summary

research topic	Single-arm, single-center, exploratory, phase II clinical study of envafolimab in full neoadjuvant treatment of pMMR / locally advanced rectal cancer with MSS
version number	V1.1
Version date	March 02, 2023
by stages	II designated time
Bid unit	And Yunnan Provincial Cancer Hospital
Principal investigator	Chief physician [name], Associate [name]
Participating in research units	Single center
subject investigated	Locally advanced rectal cancer
research design	This study is a single arm, single center, phase II, prospective clinical study to explore the efficacy and safety of envafolimab plus chemoradiotherapy in full neoadjuvant treatment of pMMR / MSS locally advanced rectal cancer.
Study duration	The study is scheduled to begin in March 2023.
Main end point	
Pathological complete response rate (pCR)	
Secondary end point	
1) R0 resection rate;	
2) Objective response rate (ORR); clinical complete response rate (cCR);	
3) Tumor downstaging rate (mrTRG); pathological downstaging rate; tumor regression grade (TRG);	
4) Anal rate;	
5) The rate of surgical complications;	
6) The 2-year disease-free survival rate (DFS);	
7) The 2-year overall survival rate (OS);	

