Effectiveness evaluation criteria	
Tumor evaluation was performed throughout the study and analyzed using the Solid Tumor Efficacy Evaluation (RECIST) criteria (version 1.1,2009). Radiological imaging (CT, MRI) scans were performed, and the clinical complete response rate (cCR), objective response rate (ORR), and tumor staging rate (mrTRG) were determined and calculated for all patients.

statistical method	
Statistical analysis was performed using SPSS23.0 or SAS software. For the PPS and FAS data, and safety indicators for the SS data. Most of the data presented in this study were descriptive. For continuous data, it is

expressed by mean and standard deviation and percentage of index index.

(1) Baseline demographic data and disease characteristics:

Characteristics of the observed patients were summarized by descriptive statistics, including age, sex, clinical stage, and ECOG scores, etc.

(2) Analysis method of the primary endpoint:

After the completion of the whole neoadjuvant treatment, two doctors in the pathology department jointly evaluated the pathological complete response rate (pCR).

(3) Secondary endpoints analysis method:

A. After the end of the whole neoadjuvant treatment, two doctors from the pathology department jointly evaluated the tumor withdrawal grade (TRG), and the pathological decline rate.

B. The imaging results were evaluated by RECIST 1.1 standard to calculate the objective response rate (ORR) and tumor descent rate (mr TRG);

C. Patient quality of life (QoL) was evaluated using the Chinese version of the Cancer Patient Quality of Life Scale [EORTC QLQ-C30] (V3.0);

D. Safety indicators: The evaluation is based on the SS set, using NCI-CTC AE v5.0 criteria, listing the incidence of adverse events and serious adverse events, their clinical presentation characteristics, severity, occurrence time, duration, treatment method, and prognosis.

E. The rate of tumor descent, the rate of anal preservation, incidence of surgical complications, incidence of adverse events and incidence of serious adverse events were all expressed in percentage.

F. Survival analysis was performed by Kaplan-Meier to estimate the 2-year overall survival (OS) and disease-free survival (DFS);

Flow chart of the clinical trial

Flow-chart description of the clinical trial

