2.2 Secondary purpose

- Objective response rate (ORR);
- Clinical complete response rate (cCR);
- Tumor downstaging rate (mrTRG);
- Downstaging rate of tumor pathology;
- Grade of tumor regression (TRG);
- R0 resection rate;
- Anal rate;
- The rate of surgical complications;
- 2-year disease-free survival rate (2-year DFS);
- 2-year overall survival rate (2-year OS);
- Quality of life (including anal sphincter function, bladder function and sexual function);
- Incidence of adverse reactions and serious adverse reactions.

The safety and tolerability of the study protocol will be evaluated according to the incidence and severity of adverse events and graded according to the NCI CTC AE 5.0 standard.

3. The research plan

This topic is a single-arm, single-center, prospective phase II clinical study.

3.1 Whole-course neoadjuvant therapy regimen:

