3.4 The Watch Wait policy

A "watchful wait" strategy (non-radical surgery) for patients whose tumor withdrawal achieved clinical complete remission (cCR) (watch-and-wait policy). Specific strategies include: digital rectal examination, tumor markers every 1 to 2 months for 2 years, thoracic, abdominal and pelvic CT, pelvic MRI, endorectal ultrasound, colonoscopy and biopsy, and even PET-CT every 3 months.

3.5 therapeutic review

1 Effectiveness: objective efficacy evaluation according to RECIST1.1 standard evaluation, divided into CR, PR, SD and PD (see 4.7 for details);

After the end of induction therapy (available), after the completion of concurrent chemoradiotherapy (available), after the end of consolidation therapy / before surgery (required) can be evaluated after neoadjuvant treatment, according to the following conditions:

- 1) The patient evaluation is CR: if anal preservation surgery is feasible, direct surgical resection; if anal preservation is impossible, after full communication and informed consent, wait for observation (wait and watch);
- 2) Patients were evaluated as PR or SD, with direct surgical resection;
- 3) The patient was evaluated as PD, but there was still possible R0 resection in preoperative evaluation, and surgical resection was performed;
- 4) If the patient is evaluated as PD and cannot be removed by R0, the replacement treatment plan should be discussed according to MDT;
- 5) If distant metastases during neoadjuvant therapy are treated in accordance with the guidelines for diagnosis and treatment of metastatic colorectal cancer.

* After completion of neoadjuvant therapy, patients must receive efficacy evaluation of the same means in the same center.

2 Surgical resection rate: R0, R1, R2 (R0 no residual tumor; R1 microscopic tumor residue; R2 gross tumor residue);

3 Safety: Observation and graded according to NCI CTC AE 5.0 toxicity criteria. Tumor markers, blood routine, blood biochemistry, and liver and kidney function were checked every 2 weeks. In the course of treatment, the occurrence of adverse reactions should be closely monitored, including edema, gastrointestinal reaction, leukopenia, anemia, hand and foot syndrome, rash, muscle spasm, diarrhea, etc., and the time,

degree, treatment methods and treatment results of adverse reactions should be recorded.

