4.7 Evaluation of the study findings

1) Efficacy evaluation of chemoradiotherapy

- CR: Pelvic MR: complete regression of primary tumor or only fibrotic scar, MR no mesangial lymph node enlargement; ultrasound colonoscopy: complete regression of primary tumor or only erythematous tiny ulcer or scar, no cancer remaining on biopsy; digital rectal tumor disappeared and no stiffness or nodules of intestinal wall.
- PR: tumor volume reduced by more than 30%, no new lesions;
- PD: tumor volume increased more than 20%, or new lesions.
- SD: The tumor volume did not change significantly, the reduction degree did not reach PR, and the increase degree did not reach PD;

2) Evaluation of the degree of radical operation

- R0 microscopic pathology examination cut margin has no residual tumor cells;
- The R1 microscopic pathological examination of the resection margin showed residual tumor cells;
- Residual tumor cells were visible at the macroscopic lower margins of R2.

3) Tumor response assessment

It is recommended to evaluate postoperative pathological specimens according to the tumor pathological withdrawal grade (tumor regression grading, TRG) criteria (see Annex 2); if not, a complete pathological response must be reported.

4) Evaluation of local recurrence or metastasis

When clinical symptoms occur (anal pain, hematochezia, lower limb edema, etc.), progressive elevation of CEA, or suspicious signs in chest or abdominal imaging, further examination is needed to find local recurrence or disease metastasis progression. Regional recurrence mainly refers to tumor recurrence in the local area or near the adjacent organs; distant metastasis refers to tumor recurrence outside the above areas. Disease-free survival is the absence of tumor recurrence or the occurrence of new colorectal cancer by systematic evaluation.

Clinical diagnosis of recurrence and metastasis must meet at least one of the following:

- 1 Imaging suggested recurrence (ultrasound, CT, MRI, PET-CT)
- 2 Positive cytology biopsy (ascites, anastomotic recurrence, suspicious imaging findings)

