2.3 Mitigation criteria

2.3.1 Evaluation of the target lesions

Complete response (CR): All target lesions disappear, and the short diameter of all pathological lymph nodes (including target nodules and non-target nodules) must be reduced to <10mm.

Partial response (PR): The sum of target lesion diameter decreased by at least 30% from baseline.

Disease progression (PD): Using the minimum value of the sum of all measured target lesions throughout the experimental study, the diameter and relative increase is at least 20% (baseline value if the minimum); otherwise, the absolute increase of at least 5mm must be met (occurrence of one or more new lesions is also considered as disease progression).

Disease stability (SD): the degree of target lesion reduction does not reach the PR, the degree of increase does not reach the PD level, in between the two, the minimum value of the sum of the diameter can be used as a reference.

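### The MRI secondary endpoint merges downstaging with mrTRG and is calculated from RECIST 1.1, which can yield only a response rate

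*Combined protocol and SAP*

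**What the plan says.** Section 2.2 lists "Tumor downstaging rate (mrTRG") as a secondary endpoint, apart from ORR and cCR. The endpoint list in the protocol summary sets it beside two pathology endpoints: "Tumor downstaging rate (mrTRG); pathological downstaging rate; tumor regression grade (TRG").

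Two rows of the summary say how it is obtained:

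- The effectiveness row names RECIST 1.1 as the criteria, mentions CT and MRI, and says that cCR, "objective response rate (ORR), and tumor staging rate (mrTRG) were determined and calculated for all patients".
- The statistical method row, item (3) B, ties the calculation to RECIST directly: "The imaging results were evaluated by RECIST 1.1 standard to calculate the objective response rate (ORR) and tumor descent rate (mr TRG"). Item (3) E adds that the rate is shown as a percentage.

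Section 3.5 describes what a RECIST evaluation returns: "objective efficacy evaluation according to RECIST1.1 standard evaluation, divided into CR, PR, SD and PD". It refers the reader to section 4.7 for detail.

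**The concern.** A named method is attached to a named endpoint, and the method does not measure it. Downstaging is a change in T or N category between two time points. mrTRG is a grade of regression read on one post-treatment MRI. RECIST is a classification of change in lesion size. The plan puts the first two under one label and derives that label from the third.

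An analyst who follows the text would report a response rate that the plan already reports elsewhere. An analyst who sees the problem would have to supply a scale, a cut-off and a denominator. In a single-arm study with no stated blinding of the imaging readers, those choices could be made with the images in view.

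The endpoint is also of use here. Under section 3.5, some patients rated CR may be observed without surgery. They have no resection specimen, so pathological stage and pathological TRG are not available for them.

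**Working it through.** The documents give no rate, threshold or power for this endpoint, so there is no figure to reproduce. The check is a comparison of texts.

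**1. What RECIST can return.** Attachment 3, section 2.3.1, works on the sum of diameters, for example: "Partial response (PR): The sum of target lesion diameter decreased by at least 30% from baseline". The target-lesion categories are CR, PR, SD and PD. The attachment adds only a not-evaluable result and a non-CR/non-PD result for special cases.

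**2. What section 4.7 adds.** Its CR category has MRI content: "CR: Pelvic MR: complete regression of primary tumor or only fibrotic scar, MR no mesangial lymph node enlargement", together with endoscopic and digital findings. PR, SD and PD are defined by change in tumour volume. The output is again the same four categories.

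**3. Rates that can be built from the four categories.**

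- CR + PR is ORR, already an endpoint.
- CR alone is close to cCR, already an endpoint.
- CR + PR + SD is disease control.
- SD or PD alone is the share of patients with that result.

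None of these is a change in T or N category, and none is a regression grade.

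**4. Whether another place supplies the missing rule.**

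- Regression scale: the only one is the 0 to 3 scale in section 6.1, which is pathological. Section 4.7 applies it to specimens: "It is recommended to evaluate postoperative pathological specimens according to the tumor pathological withdrawal grade (tumor regression grading, TRG) criteria".
- Restaging: the inclusion criteria name pelvic MRI or transrectal ultrasound for baseline staging. No section says how stage is read again after treatment or what counts as lower.
- Numerator, denominator and cut-off: item (3) E gives only the unit, a percentage.

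**5. Internal comparison.** On the pathology side, the summary and section 2.2 list downstaging and TRG as two endpoints, and item (3) A evaluates them as two items. Only the imaging side merges them. The plan's own structure therefore treats a stage change and a regression grade as different things.

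**6. Time of the scan.** Section 3.5 makes the evaluation after consolidation and before surgery mandatory, and asks for the same means of evaluation in the same centre. Section 3.7, part 2, item 11 lists pelvic MRI only after induction and after chemoradiotherapy. Item 10 does list CT before surgery. The text therefore does not settle which MRI an MRI endpoint would use.

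**The case against.** The strongest reply is that this is compressed or translated wording and not a wrong method. The endpoint is called a descent, staging and downstaging rate in different places, which look like variants of one term. Item (3) B may simply list the imaging endpoints together. The effectiveness row names RECIST in one sentence and MRI in the next, so the team may intend to grade the MRI on a scale it has not written down. Section 4.7 also brings MRI regression and nodal findings into CR, so the imaging evaluation is not purely a sum of diameters.

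Part of this stands. The naming variants are not the defect, and a rate read on an unstated MRI scale could be a valid measure. But it would not be pre-specified and would depart from the rule in item (3) B. The CR wording in section 4.7 describes one state and does not supply a scale. Translation does not explain why two quantities kept apart in pathology are joined in imaging.

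Three stronger readings are tempting and are not supported:

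- *That the background section measures the error.* Section 1.2 cites a study of 12 operated MSS patients with ORR of 100%, pCR of 58.3% (7/12 = 58.3%), three patients at grade 1 and two at grade 2 (7 + 3 + 2 = 12). Those are pathological grades from an outside study. They contain no mrTRG and no MRI downstaging. In this trial the pathological grades would be reported anyway under their own endpoints.
- *That the trial could not report MRI downstaging or regression.* Pelvic MRI is planned at baseline and during treatment (section 3.7), so both can be read once the rules exist.
- *That watch-and-wait decisions are affected.* Those rest on CR or cCR (sections 3.4 and 3.5), not on mrTRG.

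**Conclusion.** The point holds in a limited form. The stated rule cannot produce a stage change or an MRI regression grade. Followed as written, it yields ORR, a near-duplicate of cCR, or another response share. Otherwise it leaves an MRI scale open to choice after the images are seen. This is a wrong stated method as well as a missing definition.

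The effect is confined to one descriptive secondary endpoint with no test or threshold. The pCR endpoint and the sample size of 35 are unaffected. No numerical size can be given, because the documents contain no MRI stage or mrTRG data.

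The conclusion assumes that the three names for the rate refer to one endpoint, and that the flow charts, whose content is missing from the text available, do not define an MRI scale. It should be corrected before the images are analysed.

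**What to change.** 1. In the effectiveness row and item (3) B of the summary, restrict RECIST 1.1 to ORR.
2. In the summary endpoint list and section 2.2, replace the merged item with two endpoints.
3. Define MRI downstaging as a lower overall clinical stage, or a lower T or N category with neither one higher, on the post-neoadjuvant pelvic MRI than on the baseline pelvic MRI. The last condition settles patients whose T and N move in opposite directions without a lower overall stage. Naming MRI at both times matters because the inclusion criteria also allow staging by ultrasound.
4. Report mrTRG separately, on one named MRI scale with a responder cut-off fixed in advance, and state who reads the scans.
5. Use all enrolled patients as the denominator for both rates, and say how patients without a usable post-treatment MRI are counted.
6. Reconcile section 3.5 with section 3.7, part 2, item 11 on the time of the MRI. If no pre-surgery MRI is intended, name the post-chemoradiotherapy scan as the one used for both endpoints.

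The cost is wording plus two case report form fields read from MRI. No new procedure is needed if the post-chemoradiotherapy scan is used, or if the evaluation before surgery already includes MRI. If it does not and a pre-surgery MRI is wanted, that scan is an added cost.
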